10.2 STRATIFICATION AND COVARIATE ADJUSTMENT

None.

10.3 INTERACTIONS

None.

10.4 MISSING DATA

No methods to account for missing safety data will be used.

In the instance of missing pharmacokinetic blood samples, the trapezoidal rule will be employed between the samples immediately before and after the missing sample for the AUC calculations.

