Participants will be admitted to the Clinical Unit on the morning of Day-1 with confirmation of eligibility and baseline assessments performed as per Table 10.9.3. Randomisation will occur prior to dose on Day 1. An evening snack will be consumed at least 10 h before each dose administration. After an overnight fast of at least 10 h, dose administration will occur each day, on the morning of Day 1 to Final Dosing Day (planned as Day 10). It is planned to administer doses in Part C in a fasted state, however following review of Part B food-effect data, the dose *may* be administered in a fed state with a standardised meal. Fasting will continue until 4 h post-dose; a standardised meal will then be provided. Clinical and laboratory assessments of safety, tolerability and PK variables will be conducted throughout the in-house period as per Table 10.9.3.

Participants will be discharged from the Clinical Unit on Post-Treatment (i.e., Day 13) following the completion of the 72 h post-last dose assessments providing there are no ongoing safety concerns.

Post-Study Follow Up Visit (5-7 days after final dose of IMP i.e., Day 17).

For participants in all MAD cohorts, a follow-up visit will be conducted 5-7 days following last IMP or placebo administration. If all follow-up assessments (Table 10.9.3.) are satisfactory the PI (or delegate), will discharge the participant from the study. If any AEs are ongoing, or any assessments are not satisfactory, participants may be recalled to the unit for follow-up assessments until the PI (or delegate) is satisfied the participant is medically stable and may be discharged from the study. Participants will be advised to return or contact the unit at any time if they may be experiencing any adverse effects.

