3.1 OVERVIEW

This is a phase I, randomised, double-blind, placebo-controlled study to investigate the safety, tolerability, and PK of AX-158 in healthy male participants following single (Part A) and multiple (Part C) ascending doses including food effect (Part B).

The study will be conducted in three parts:

Part A

Part A (SAD) will enrol up to 8 participants per cohort randomised (3:1) to receive AX-158 or placebo. Part A will follow a single ascending dose (SAD) design with all participants receiving one dose of AX-158 (or placebo) in the fasted state.

This part will be conducted in up to 34 participants (8 participants in cohorts 1 and 5, 6 participants in cohorts 2, 3 and 4). An additional two cohorts of up to eight (8) participants each (up to 16 additional participants total) may be investigated if required.

Part B

Part B (Food Effect) will be conducted in up to 8 participants in a cross-over manner; each participant will receive AX-158 in the fed and fasted state.

This part will be conducted in up to 8 participants in a cross-over manner.

Part C

Part C (MAD) will enrol up to 8 participants per cohort randomised to (3:1) to receive AX-158 or placebo. Part C will follow a multiple ascending dose (MAD) design with participants receiving AX-158 (or placebo) once daily for 10 consecutive days, in a fed or fasted state (depending on the outcome of the Part B (Food Effect)). Doses, dosing duration and dose regimen (i.e., q.i.d., b.i.d., t.i.d.) of AX-158 and matching placebo for Part C may be modified based on all available safety, tolerability, and PK data and applied to additional MAD cohorts.

This part will be conducted in up to twenty-four (24) participants (3 cohorts of up to 8 participants). An additional two cohorts of up to eight (8) participants each (up to 16 additional participants total) may be investigated if required.

Duration of study:

- Part A: approximately 6 weeks for each individual (from the screening to post-study follow-up).
- Part B: approximately 8 weeks for each individual (from the screening to post-study follow-up).
- Part C: approximately 7 weeks for each individual (from the screening to post-study follow-up).

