11.4 PK ANALYSES

11.4.1 Concentration Data

Plasma PK samples will be collected for the measurement of AX-158 at the following time points:

Part A:

- Day 1 pre-dose, 30 mins, 45 mins, 1h, 2h, 3h, 4h, 6h, 8h, 12h
- Day 2: 24h, 36h
- Day 3: 48h
- Day 4: 72h

Part B: For both treatment periods

- Day 1 pre-dose, 30 mins, 45 mins, 1h, 2h, 3h, 4h, 6h, 8h, 12h
- Day 2: 24h, 36h
- Day 3: 48h
- Day 4: 72h

Part C:

- Day 1 and Day 10 pre-dose, 1h, 2h, 3h, 4h, 5h, 6h, 8h, 12h
- Day 2 and Day 11: 24h, 36h
- Day 3 and Day 12: 48h
- Day 4 and Day 13: 72h
- Day 5: pre-dose
- Day 6: Pre-dose
- Day 7: Pre-dose
- Day 8: Pre-dose

Plasma AX-158 concentrations will be listed along with blood sampling times and details of any sampling time deviations and summarised for each treatment using the descriptive statistics N, n, arithmetic mean,

geometric mean, arithmetic standard deviation (SD), coefficient of variation (CV%), minimum, median and maximum.

The individual subject plasma AX-158 concentration profiles over time will be presented graphically on both linear and semi-logarithmic scales with each subject on a separate plot. For Part C, Day 1 and Final Dosing Day (Day 10) profiles will be presented on the same plot. The geometric mean plasma AX-158 concentration profiles over time will be presented graphically on both linear and semi-logarithmic scales with all treatments on the same plot, with separate plots for Day 1 and Final Dosing Day profiles for Part C.

Urine PK samples will be collected for the measurement of AX-158 at the following time intervals: pre-dose and in intervals of 0-12, 12-24, 24-48 and 48-72 h post-dose on Day 1 and Day 10.

Urine AX-158 concentrations will be listed along with urine volumes and summarised for each treatment using the descriptive statistics N, n, arithmetic mean, geometric mean, arithmetic standard deviation (SD), coefficient of variation (CV%), minimum, median and maximum.

For inclusion within the summary tables and plots, plasma and urine concentrations below the lower limit of quantification (LLOQ) will be imputed as zero at pre-dose and as LLOQ/2 for post-dose samples. They will be listed as recorded. Data reported as not reportable or no sample/result will be handled as missing (i.e. no assumption will be made about the actual concentration).

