AUC_{0-24} ($\text{h}^*\mu\text{g/mL}$)	Area under the concentration-time curve (AUC) from the time of dosing to 24 h post-dose	AUC measured from the concentration at time of dosing to 24 hours post dose. The AUC is computed using the linear up-log down trapezoidal rule.	AUC0-24
$AUC_{0-\tau}$ ($\text{h}^*\mu\text{g/mL}$) (only required if non-q.d. dosing regimen)	Area under the plasma concentration-time curve (AUC) from the time of dosing to $<X>$ hours (dosing interval) after the Day $<X>$ dose.	AUC measured from the concentration at time of dosing to the concentration at $<X>$ hours. The AUC is computed using the linear up-log down trapezoidal rule.	AUC_TAU

Part C on Final Dosing Day:

Pharmacokinetic Parameter and Unit	Definition	Computation	WinNonlin Parameter Name
C_{max} ($\mu\text{g/mL}$)	Maximum concentration.	Maximum observed concentration, occurring at T_{max} . If not unique, then the first maximum is used.	Cmax
T_{max} (h)	The time to maximum observed concentration.	Time of maximum observed concentration. If the maximum observed concentration is not unique, then the first maximum is used.	Tmax

Pharmacokinetic Parameter and Unit	Definition	Computation	WinNonlin Parameter Name
λz (1/h)	Elimination rate constant.	First order rate constant associated with the terminal (log-linear) portion of the curve. Estimated by linear regression of time vs. log concentration; the regression analysis should contain data from at least 3 different time points in the terminal phase	lambda_z
$t_{1/2}$ (h)	Terminal elimination half-life.	$= \ln(2) / \lambda z$	HL_Lambda_z
AUC_{0-24} (h* μ g/mL)	Area under the concentration-time curve (AUC) from the time of dosing to 24 h post-dose	AUC measured from the concentration at time of dosing to 24 hours post dose. The AUC is computed using the linear up-log down trapezoidal rule.	AUC0-24
$AUC_{0-\tau}$ (h* μ g/mL) (only required if non-q.d. dosing regimen)	Area under the plasma concentration-time curve (AUC) from the time of dosing to 24 hours (dosing interval) after the Day 10 dose.	AUC measured from the concentration at time of dosing to the concentration at 24 hours. The AUC is computed using the linear up-log down trapezoidal rule.	AUC_TAU

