Pharmacokinetic Parameter and Unit	Definition	Computation	WinNonlin Parameter Name
Ae (µg)	Cumulative amount of study drug excreted in urine during a time interval.	The sum of the individual urine volume * urine concentration of study drug. $= \Sigma (\text{Concentration} \cdot \text{Volume})$	N/A (calculated using SAS)
Ae% (%)	Percentage of study drug excreted in urine during a time interval.	$= 100 \cdot Ae / \text{Dose}$	N/A (calculated using SAS)
CLR (L/h)	Renal clearance.	$= Ae / AUC_{0-t}$	N/A (calculated using SAS)

The derived urine pharmacokinetic parameters Ae, Ae%, CumAe, CumAe%, CLR will be determined from the individual urine concentration versus time data using SAS EG v8.3 or higher.

Derived PK parameters will be listed along with the points used to calculate λz (lower, upper, and number used) and coefficient of determination (R^2) adjusted. The derived PK parameters will also be summarised. The descriptive statistics presented will be N, n, arithmetic mean, geometric mean (with the exception of T_{\max}), SD, coefficient of variation (CV%), minimum, median, and maximum.

Any $AUC_{\% \text{ extrap}}$ values greater than 20% will be flagged within the data listing. In accordance with regulatory guidance, the associated data should not be excluded from analysis but if this is observed for >20% of the profiles, the validity of the study may be in question.

In the instance of a significant sample time deviation ($\geq 5\%$ of nominal time i.e. 72 min) for the 24 h PK sample, the AUC_{0-24} values will be excluded from statistical analysis, but will be calculated, included in the derived PK data listing and flagged. Where a non-significant sample time deviation (≤ 72 min) for the 24 h PK sample occurs and the terminal elimination rate constant (λz) is estimable, this will be used to estimate AUC_{0-24} . Where a non-significant sample time deviation (≤ 72 min) for the 24 h PK sample occurs and the terminal elimination rate constant (λz) is not estimable, WNL is unable to estimate AUC_{0-24} . Therefore, in order for an AUC_{0-24} value to be estimated, the actual sampling time (including bleed time deviations) at the 24 h nominal time point will be used for the partial AUC settings.

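### SAP 10.4 bridges a missing PK sample without excepting an intervening dose, so a missing 24 h sample in the Part C Day 1 profile would be interpolated across dose 2 and overstate that participant's Day 1 AUC0-24

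*SAP*

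**What the plan says.** SAP 10.4 gives a single rule for missing PK blood samples: "the trapezoidal rule will be employed between the samples immediately before and after the missing sample for the AUC calculations". It is not limited by study part, day or dosing interval.

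SAP 11.4.1 lists the Part C plasma samples as "Day 1 and Day 10 pre-dose, 1h, 2h, 3h, 4h, 5h, 6h, 8h, 12h", followed by "Day 2 and Day 11: 24h, 36h", with 48 h and 72 h after that. Protocol Table 10.9.3 also has samples at 12, 24 and 36 h.

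On dosing, SAP 3.1 has "participants receiving AX-158 (or placebo) once daily for 10 consecutive days". Protocol 10.1 agrees: "dose administration will occur each day, on the morning of Day 1 to Final Dosing Day", planned as Day 10. The supplied protocol is version 4.0 and the SAP cites version 5.0, but the SAP's own text confirms once-daily dosing.

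For Part C Day 1 under once-daily dosing, SAP 11.4.2 derives only Cmax, Tmax and AUC0-24. It defines AUC0-24 as "AUC measured from the concentration at time of dosing to 24 hours post dose" and computes it by the linear-up/log-down rule. The section has a special rule for a mistimed 24 h sample: at 72 min or more off nominal time, the AUC0-24 "values will be excluded from statistical analysis, but will be calculated, included in the derived PK data listing and flagged". It has no rule for a 24 h sample that was never obtained.

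**The concern.** Joining the neighbours is reasonable when nothing is given between them. That is so in Part A, in each period of Part B, and after the last Part C dose on Day 10. It is not so on Part C Day 1. There the 24 h draw coincides with dose 2 (taken here to be pre-dose), and the 36 h draw comes about 12 h after it. Bridging from 12 h to 36 h replaces the first-dose trough with a value raised by the second dose.

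The stake is the Day 1 AUC0-24, a secondary variable and one of three Day 1 plasma parameters. Protocol 10.8.9 also compares individual AUC0-24 values with an exposure limit when escalation is considered.

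**Working it through.** The plan states no figure for this point, so there is none to reproduce.

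**Inputs from the documents:** sample times 0, 1, 2, 3, 4, 5, 6, 8, 12, 24 and 36 h; doses at 0 and 24 h; linear-up/log-down trapezoid; 6 active participants per cohort as planned.

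**Assumptions:** one compartment, first-order absorption, linear kinetics and no noise. Half-life is 2 to 36 h and ka is 0.5 or 1.5 per h. The protocol reports no earlier human data, so these are ranges and not estimates.

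**Direction.** Let c(t) be the concentration after a single dose. By superposition C36 = c(12) + c(36), and C12 = c(12). So C36 is at least C12, and the 12 to 36 h segment is treated as rising and interpolated linearly:

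bridged C24 = (C12 + C36)/2 = C12 + c(36)/2.

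This is at or above C12. The true C24 is below C12 once concentrations are falling by 12 h. Under these assumptions the error is therefore always upward.

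**Worked case, half-life 12 h, ka 1.5 per h (dose/volume set to 1).**
- C12 = 0.520, true C24 = 0.260, C36 = 0.520 + 0.130 = 0.650.
- Bridged C24 = (0.520 + 0.650)/2 = 0.585.
- True AUC12-24, log rule: 12 × (0.520 − 0.260)/ln 2 = 4.50.
- Bridged AUC12-24, linear rule: 12 × (0.520 + 0.585)/2 = 6.63.
- AUC0-24 goes from 12.69 to 12.69 + 2.13 = 14.82, and 14.82/12.69 = 1.168, or +16.8%.

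**Overstatement of AUC0-24 over the range.**

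| Half-life (h) | ka 0.5 per h | ka 1.5 per h |
|---|---|---|
| 2 | +13.7% | +6.8% |
| 4 | +23.4% | +17.9% |
| 6 | +23.1% | +19.4% |
| 8 | +21.4% | +18.7% |
| 12 | +18.6% | +16.8% |
| 24 | +15.5% | +14.4% |
| 36 | +14.6% | +13.7% |

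**Cohort geometric mean, one affected participant in 6.** The factor is the individual ratio to the power 1/6: 1.068^(1/6) = 1.011 and 1.234^(1/6) = 1.036, or about 1% to 4%.

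**Controls.** The same bridge was applied where no dose falls at 24 h, to a single-dose profile and to the Day 10 profile. It changed AUC0-24 by less than 0.1% in both, so the intervening dose is the cause.

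**Individual Day 10/Day 1 ratio in the worked case.** It falls from 1.35 to 1.35/1.168 = 1.16. The verdict says where this figure could and could not appear.

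**The case against.** The strongest reply is that the Day 1 profile may be meant to stop at 24 h. Day 1 has only Cmax, Tmax and AUC0-24, with no terminal rate constant. If the 36, 48 and 72 h samples belonged to the profile, the search for Day 1 Cmax would run over concentrations following doses 2 and 3. SAP 11.4.2 also says the software cannot produce AUC0-24 when the 24 h sample is slightly mistimed and the terminal rate is not estimable, which fits a profile ending at 24 h. (It fits equally well a Part A or B profile whose later samples are below quantification.) This reading is plausible, but it is inference, and no section states it. If it is right, a missing 24 h sample has no later neighbour and 10.4 gives no method at all. A clarification is needed either way.

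General safeguards exist. The PK Set asks for sufficient profiles and, in Part C, a valid Day 1 profile (SAP 6.3). Escalation counts only participants with enough samples to estimate AUC0-24 (SAP 7). SAP 10.1 allows documented alternative methods. These leave the case to judgement and do not name the 24 h sample.

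It also stands that the trigger should be rare. Participants are resident, PK draws take first priority (protocol 10.9.1), and an unsuitable sample may be repeated once (protocol 10.9.23). The cohort shift is small beside sampling error: with an assumed CV of 25% and n = 6, the standard error of a geometric mean is about 0.25/√6 = 10%. For the individual exposure limit, an overstated value errs toward caution.

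**Conclusion.** The gap is real and minor. Read literally, SAP 10.4 bridges a dose in the Part C Day 1 profile and overstates the affected participant's AUC0-24 by about 7% to 23%. With one affected participant in 6, the cohort geometric mean rises by about 1% to 4%. These sizes depend on the assumed half-life, absorption rate and one-compartment form, and on the 24 h sample being missing or unusable. The upward direction follows from superposition, given linear kinetics and falling concentrations after 12 h.

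Under once-daily dosing the effect reaches listed and summarised Day 1 AUC0-24 and any exposure review using those values.

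Two stronger readings are not supported:
- **A reader might infer that the planned accumulation analysis is biased toward no accumulation.** SAP 11.4.3.4 analyses Cmax, and AUC0-tau only for regimens other than once daily. The Part C dose-proportionality section (11.4.3.2) does not use AUC0-24 either. The lower Day 10/Day 1 ratio therefore concerns informal comparisons. The exception would be if AUC0-tau is reported under once-daily dosing, as the shell for Table 14.4.2.6 shows with its once-daily footnote.
- **A reader might infer that the SAP contradicts itself**, because a mistimed 24 h sample is handled more strictly than an absent one. The 11.4.2 rule covers timing only and removes the value from statistical analysis, not from listings. In Part C under once-daily dosing, AUC0-24 enters no specified statistical analysis. This is an asymmetry with little practical effect there, not a contradiction.

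**What to change.** Add to SAP 10.4:
- Interpolation is not made across an intervening dose.
- The Part C Day 1 profile uses only samples taken before the second dose.
- If the Day 1 24 h sample is missing or unusable, C24 is estimated by log-linear extrapolation of the declining samples before dose 2, but only where the existing 11.4.2 criteria are met: at least 3 points excluding Cmax and adjusted R² of at least 0.85. The resulting AUC0-24 is flagged in the listing.
- Otherwise Day 1 AUC0-24 is set to missing.

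The cost is a few lines of SAP text and a profile setting in the PK software. The downside is an occasional missing or extrapolated Day 1 AUC0-24. With draws at 6, 8 and 12 h, a Tmax of 5 h or earlier leaves at least three later points. A Tmax of 6 h leaves two, so the value would be missing. Log-linear extrapolation is close to exact in the noise-free one-compartment model by construction. That says nothing about noisy or multiphasic profiles, which is why the fit criteria and the flag should be kept.

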10.5 POOLING OF SITES

Not applicable.

10.6 MULTIPLE COMPARISONS

No multiplicity adjustments are planned.

10.7 SUBGROUP ANALYSES

None.

10.8 STATISTICAL ISSUES

None.

11 STATISTICAL OUTPUT

General principles for layout of the statistical output are described in Section 10.1. Layout and specifications are illustrated for each unique table in the table shells in Section 14.

11.1 SUBJECT DISPOSITION

The subject disposition table will summarise the following data:

- The number of consented subjects
- The number of subjects receiving each treatment
- The number (%) of subjects who completed/withdrew from the study and the associated reasons for withdrawal
- The number (%) of subjects in each analysis set

All percentages will be calculated from the number of dosed subjects within a treatment group for Parts A and C or number of dosed subjects for Part B.

Screening and study completion/termination data (including informed consent information) will also be listed. A listing of all protocol deviations will be presented including major/minor classification. A data listing presenting subject eligibility for each analysis set and the reason for exclusion from an analysis set will also be presented.

Disposition data will be listed and summarised for the All Consented Set.

11.2 SUBJECT CHARACTERISTICS AT BASELINE

11.2.1 Demographic and Baseline Characteristics

Demographic data will be listed. Descriptive statistics (number of participants in the analysis set (N), number of participants with non-missing observations (n), mean, standard deviation (SD), minimum, median, and maximum) will be tabulated for the continuous variables age, height, weight and BMI at Screening and frequencies (number and %) for the categorical variables race and ethnicity.

Demographic data will be listed and summarised using the Safety Set.

11.3 EFFICACY ANALYSES

Not applicable.

11.4 PK ANALYSES

11.4.1 Concentration Data

Plasma PK samples will be collected for the measurement of AX-158 at the following time points:

Part A:

- Day 1 pre-dose, 30 mins, 45 mins, 1h, 2h, 3h, 4h, 6h, 8h, 12h
- Day 2: 24h, 36h
- Day 3: 48h
- Day 4: 72h

Part B: For both treatment periods

- Day 1 pre-dose, 30 mins, 45 mins, 1h, 2h, 3h, 4h, 6h, 8h, 12h
- Day 2: 24h, 36h
- Day 3: 48h
- Day 4: 72h

Part C:

- Day 1 and Day 10 pre-dose, 1h, 2h, 3h, 4h, 5h, 6h, 8h, 12h
- Day 2 and Day 11: 24h, 36h
- Day 3 and Day 12: 48h
- Day 4 and Day 13: 72h
- Day 5: pre-dose
- Day 6: Pre-dose
- Day 7: Pre-dose
- Day 8: Pre-dose

Plasma AX-158 concentrations will be listed along with blood sampling times and details of any sampling time deviations and summarised for each treatment using the descriptive statistics N, n, arithmetic mean,

geometric mean, arithmetic standard deviation (SD), coefficient of variation (CV%), minimum, median and maximum.

The individual subject plasma AX-158 concentration profiles over time will be presented graphically on both linear and semi-logarithmic scales with each subject on a separate plot. For Part C, Day 1 and Final Dosing Day (Day 10) profiles will be presented on the same plot. The geometric mean plasma AX-158 concentration profiles over time will be presented graphically on both linear and semi-logarithmic scales with all treatments on the same plot, with separate plots for Day 1 and Final Dosing Day profiles for Part C.

Urine PK samples will be collected for the measurement of AX-158 at the following time intervals: pre-dose and in intervals of 0-12, 12-24, 24-48 and 48-72 h post-dose on Day 1 and Day 10.

Urine AX-158 concentrations will be listed along with urine volumes and summarised for each treatment using the descriptive statistics N, n, arithmetic mean, geometric mean, arithmetic standard deviation (SD), coefficient of variation (CV%), minimum, median and maximum.

For inclusion within the summary tables and plots, plasma and urine concentrations below the lower limit of quantification (LLOQ) will be imputed as zero at pre-dose and as LLOQ/2 for post-dose samples. They will be listed as recorded. Data reported as not reportable or no sample/result will be handled as missing (i.e. no assumption will be made about the actual concentration).

For inclusion within the summary tables and figures, when calculating the geometric mean concentrations at pre-dose where zero values are likely to be observed, a small value (e.g. 0.001 or smaller) will be added to all individual subject pre-dose concentration values prior to calculation of the mean. This value will then be subtracted after back-transformation, i.e.

$$\text{Geometric Mean} = \exp\left(\frac{1}{n} \sum_{i=1}^n \log(x_i + 0.001)\right) - 0.001$$

where x_i are the individual concentration values at pre-dose.

This method is only required for pre-dose results as zero values will not occur for post-dose time points (due to the above imputation method of BLQ values). For post-dose time points, the geometric mean will be calculated using the standard formula:

$$\text{Geometric Mean} = \exp\left(\frac{1}{n} \sum_{i=1}^n \log(x_i)\right).$$

Concentration data listings and individual plots will be presented using the Safety Set. Concentration data summaries and mean plots will be presented using the PK Set. All concentration data included in listings and summaries will be presented to 3 significant figures.

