10.11.8 PK Data

Concentration-Time Data: Individual plasma and urine AX-158 concentration-time data will be listed. Plasma and urine concentration-time data will also be summarised. The descriptive statistics presented will be N, n, arithmetic mean, geometric mean, SD, coefficient of variation (CV%), minimum, median, and maximum. Individual and mean plasma concentration-time data will also be plotted on both linear and semi-logarithmic scales.

For the purposes of summarising and plotting concentration-time data, concentration value(s) below the LLOQ will be assigned a value of zero if the timepoint is prior to treatment and LLOQ/2 otherwise.

Derived PK Data: The following PK parameters will be derived from plasma and urine AX-158 concentration-time data following administration of IMP using Phoenix WinNonlin (the most up to date version will be used and this will be documented in the SAP). Additional parameters may be reported as appropriate.

For the purposes of calculating PK parameters, concentration value(s) below the LLOQ will be assigned a value of missing.

Plasma:

- C_{\max} Maximum concentration.
- T_{\max} The time to maximum observed concentration.
- T_{lag} The delay in achieving T_{\max}
- λ_z Elimination rate constant.
- $t_{1/2}$ Terminal elimination half-life.
- AUC_{0-24} Area under the concentration-time curve (AUC) from 0 to 24 h post-dose.
- $AUC_{0-\tau}$ Area under the concentration-time curve (AUC) from 0 to τ , where τ is the dosing interval (planned, 0 - 24 h) (Part C only).
- AUC_{0-t} Area under the concentration-time curve (AUC) from the time of dosing to the time of the last measurable concentration.
- $AUC_{0-\infty}$ AUC extrapolated to infinity.
- $AUC\%$ extrapolated Residual area.
- CL/F Total apparent clearance following extravascular administration.
- V_z/F Apparent volume of distribution following extravascular administration.

Urine

- A_e Amount and cumulative amount of dose excreted in urine over each collection interval.
- $A_e\%$ % and cumulative % of dose excreted in urine over each collection interval.
- CL_R Renal clearance.

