11.4.3.3 Part C (MAD) - Steady State

For each treatment, log-transformed trough concentration levels at pre-dose on Day 5 and Final Dosing Day (Day 10) will be subjected to a mixed effects analysis of variance (ANOVA) with study day as a fixed effect and subject as a random effect in order to establish whether steady-state has been attained for each treatment. The point and interval estimates will be back-transformed to give estimates of the ratios of the geometric LSMeans and corresponding 90% CIs for the comparisons of each consecutive day (i.e. Day 10/Day 5). In addition, estimated geometric LSMeans and corresponding 95% CIs will be presented for each study day.

The geometric LSMean ratio and corresponding 90% CI for the Day 10/Day 5 comparison will be presented graphically (a plot with error bars) with all treatments on one graph. On the same graph, points indicating individual within-subject ratios for the comparison will be presented.

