Lower Limit of Quantitation - XX.XX <units>.

Programming Note: For Part B, treatment will be included as a column within the listing.

AX-158-101

Figure 16.2.5.1

Individual Plasma AX-158 Concentration-Time Curves on a Linear Scale
Safety Set

Part <X> (<SAD/Food Effect/MAD - Cohort <X>: <Treatment>

Figure Specifications

By: Treatment with all subjects on one plot, and also study day for Part C, with a separate plot for each PK profile day. For Part B, one plot per subject presenting all treatments.

x axis: Time
x axis: Label: Time (h)
x axis: values: 0 to last sampling time point (present sampling time points only)

Y axis: AX-158 concentration
Y axis Label: AX-158 Conc. (<units>)
Y axis values: As appropriate

Legend N/A

Source Listing: 16.2.5.1; Produced: yyyy-mm-ddThh:mm - Page x of y

Treatment: <appropriate treatment footnote for study part>

Lower Limit of Quantification = xx.xx <units>. BLQ values set to zero at pre-dose and LLOQ/2 for post-dose samples.

In order to capture the zero values within the calculation of the geometric mean, a value of 0.001 was added to all Day 1 pre-dose values prior to log-transformation. The geometric means were then calculated and 0.001 subtracted from the estimate, i.e. geometric mean = $\exp(\text{mean of log(concentration+0.001)}) - 0.001$.

Programming note: Similar figures will be produced for Individual Plasma AX-158 Concentration-Time Curves on a Semi-Logarithmic Scale (Figure 16.2.5.2).

Version: 3.0
Document Title: SAP Template - Phase 1
Document Number: TEMP-00109
Previous Document Number: STATt008

AX-158-101
Listing 16.2.5.2
Individual Derived Plasma AX-158 Pharmacokinetic Parameters
Safety Set

Part <X> (<SAD/Food Effect/MAD - Cohort <X>: <Treatment>)

Subject	Visit	Parameter	Value	Unit
xxx	xxxxxxxx	xxxxxxxxxx	x.x	xxxx
		xxxxxxxxxx	x.x	xxxx
		xxxxxxxxxx	x.x	xxxx
		xxxxxxxxxx	x.x	xxxx
		xxxxxxxxxx	x.x	xxxx
		xxxxxxxxxx	x.x	xxxx
xxx	xxxxxxxx	xxxxxxxxxx	x.x	xxxx
		xxxxxxxxxx	x.x	xxxx
		xxxxxxxxxx	x.x	xxxx
		xxxxxxxxxx	x.x	xxxx
		xxxxxxxxxx	x.x *	xxxx
		xxxxxxxxxx	x.x	xxxx

Produced: yyyy-mm-ddThh:mm - Page x of y

Treatment: <appropriate treatment footnote for study part>

Lower Limit of Quantification = xx.xx <units>. For the purposes of PK parameter calculation, BLQ values were set to zero at pre-dose and missing for post-dose time points.

* AUC%extrap value greater than 20%.

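### The SAP's rule for values below the LLOQ turns Part C on-treatment troughs into zeros in the summaries and plots, and the steady-state ANOVA has no such rule

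*SAP*

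**What the plan says.** **Summaries and plots, SAP 11.4.1.** The sentence opens "For inclusion within the summary tables and plots, plasma and urine concentrations below the lower limit of quantification (LLOQ") and goes on to say that these values "will be imputed as zero at pre-dose and as LLOQ/2 for post-dose samples". Pre-dose is not limited to Day 1. The same section lists Part C pre-dose samples on Days 1, 5, 6, 7, 8 and 10.

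**Summaries and plots, protocol V4.0, 10.11.8.** A value below the LLOQ "will be assigned a value of zero if the timepoint is prior to treatment and LLOQ/2 otherwise".

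**Geometric mean, SAP 11.4.1.** Where pre-dose zeros are likely, a small value, given as 0.001 or smaller by way of example, "will be added to all individual subject pre-dose concentration values prior to calculation of the mean". It is subtracted again after back-transformation.

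**Shell footnotes, SAP 15.** The footnote to Table 14.4.1.1, a table to be repeated for Part C, applies the offset to every pre-dose value. The footnote to Figure 16.2.5.1 says "a value of 0.001 was added to all Day 1 pre-dose values". The concentration shells leave the unit as a placeholder.

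**PK parameters.** SAP 11.4.2 sets values below the LLOQ to zero at pre-dose and to missing afterwards. In protocol 10.11.8, for parameter calculation, a "concentration value(s) below the LLOQ will be assigned a value of missing".

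**Steady state, SAP 11.4.3.3.** The mixed ANOVA uses "log-transformed trough concentration levels at pre-dose on Day 5 and Final Dosing Day (Day 10"). It does not say what to do with a value below the LLOQ.

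**Declared changes, SAP 1.2.** Two changes from the protocol are listed. Neither concerns values below the LLOQ.

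**The concern.** Zero is a sensible value before any drug has been given. A Part C trough on Day 5 or Day 10 follows four or nine daily doses, so a value below the LLOQ there means little drug, not none. As worded, the SAP gives both samples the same zero.

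The rule also treats like samples differently. The Part C samples labelled 24 h on Days 2 and 11 are taken as long after a dose as the Day 5 or Day 10 trough, yet they would receive LLOQ/2. Only the label differs.

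Two things are at stake. The trough geometric mean becomes a function of a constant that the programmer chooses. And the steady-state comparison, with six active subjects per cohort, would need a decision after the data are seen.

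**Working it through.** The documents give no figure on this point to reproduce. The LLOQ is not stated, so the numbers are illustrative.

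**1. Geometric mean of a trough**

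Inputs: six active subjects per Part C cohort (SAP 3.3); assumed LLOQ 1 ng/mL; five troughs at 5 ng/mL and one below the LLOQ.

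Protocol rule: GM = (5^5 × 0.5)^(1/6) = 3.41 ng/mL.

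SAP rule: GM = exp(mean of log(x + d)) − d, with the low value at zero.

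- d = 0.001, data in µg/mL (1 ng/mL): (6^5 × 1)^(1/6) − 1 = 3.45 ng/mL
- d = 0.0001, data in µg/mL (0.1 ng/mL): (5.1^5 × 0.1)^(1/6) − 0.1 = 2.55 ng/mL
- d = 0.001, data in ng/mL: (5.001^5 × 0.001)^(1/6) − 0.001 = 1.21 ng/mL

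With two of six below the LLOQ, the same three settings give 2.30, 1.28 and 0.29 ng/mL, against (5^4 × 0.5^2)^(1/6) = 2.32 under LLOQ/2.

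For small d, each tenfold change in d moves the result by about 10^(k/6) when k of six are below the LLOQ: 1.47-fold for k = 1 and 2.15-fold for k = 2. With k = 0 and equal values the offset cancels exactly.

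**2. Steady-state ANOVA**

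log(0) is undefined, so neither of the SAP's two rules, each giving zero at pre-dose, can supply a value here. To see how much the choice matters, take invented troughs in ng/mL:

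- Day 5: below LLOQ, 3, 3.5, 4, 4.5, 5
- Day 10: 3, 3.3, 3.6, 4.2, 4.4, 5.2

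For complete pairs the ANOVA reduces to a paired t-interval on log(Day 10/Day 5). The ratio and 90% CI are:

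- affected subject excluded: 1.04 (1.00 to 1.08)
- LLOQ/2 = 0.5 substituted: 1.39 (0.77 to 2.51)
- 0.001 ng/mL substituted: 3.92 (0.27 to 57.0)

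**3. Are troughs below the LLOQ plausible?**

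This is a rough guide only. Protocol Table 10.8.2 projects an AUC of 0.38 µg·h/mL at 5 mg. Protocol 8.7 puts Cmax at the starting dose 78-fold below the male minipig NOAEL value. If 3.26 µg/mL is that value (an assumption), Cmax = 3.26/78 = 0.0418 µg/mL.

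Assume one compartment with first-order absorption and Tmax of 1, 2 or 3 h:

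- ke·exp(−ke·Tmax) = 0.0418/0.38 gives ke = 0.125, 0.148, 0.201 per h.
- ln(ka/ke)/(ka − ke) = Tmax gives ka = 3.44, 1.19, 0.51 per h.
- Steady-state trough = AUC·ke·[ka/(ka − ke)]·[e^(−24ke)/(1 − e^(−24ke)) − e^(−24ka)/(1 − e^(−24ka))] = 2.6, 1.9, 1.0 ng/mL.

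Three times the dose, 15 mg, gives 7.8, 5.7 and 3.0 ng/mL. At an LLOQ of 1 ng/mL a typical trough would be measurable, if only just in the lowest case. Individual low values are possible, and a higher LLOQ would make them likelier.

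**The case against.** **Scope.** A reader might infer that the SAP sends zeros into the steady-state ANOVA, so that the lowest troughs drop out and the result is biased. The text does not support this. The zero rule is limited to summary tables and plots, the offset to summary tables and figures, and 11.4.3.3 is silent. What stands is a missing rule.

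**Protocol.** A reader might also infer that the protocol requires LLOQ/2 in that ANOVA. It does not: its LLOQ/2 rule covers summarising and plotting, and its steady-state paragraph gives no rule. The conflict over summaries is shown only against V4.0. The SAP was written from V5.0, and its sampling schedule differs visibly from V4.0, so SAP 1.2 may be complete against the later text. V4.0 does not define its phrase for before treatment, although SAP 11.6.1 uses a similar label for events before first administration.

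**Size.** With the printed 0.001 and data in µg/mL (the unit SAP 11.4.2 gives for Cmax), the example differs by about 1% (3.45 against 3.41). The larger differences need a smaller offset or ng/mL. That is fair, but the SAP permits a smaller offset and leaves the concentration unit open. The close agreement is also accidental: it arises because an offset of 1 ng/mL happens to lie near the assumed LLOQ.

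**Intent.** The Day 1 footnote may show what was meant, and it sits on an individual-profile figure where no geometric mean is computed, so it may be leftover text. The rule itself and the other footnotes still say otherwise.

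**Impact.** Individual values are listed as recorded, medians are reported, PK is secondary, and no formal hypothesis testing is planned. This limits the consequence but does not make the rule right.

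**Conclusion.** The point holds for the Part C summaries and plots. Followed literally, SAP 11.4.1 gives zero to an on-treatment trough below the LLOQ. That departs from protocol V4.0 and leaves the geometric mean dependent on an unfixed offset and unit. In the six-subject example the result ranges from 1.21 to 3.45 ng/mL, against 3.41 under the protocol's rule.

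For the steady-state ANOVA the finding is narrower: no rule exists, the SAP's two existing rules give a value that cannot be logged, and the choice can move the estimated ratio materially.

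All of this is conditional on at least one trough being below the LLOQ, which the documents neither establish nor exclude: LLOQ, observed half-life and Part C doses are not given. SAP 1.2 does foresee profiles wholly below the LLOQ. A fixed loss of precision should not be inferred either. Losing one of six pairs widens the 90% interval by about 16% only if the SD is unchanged; in the example above, excluding the pair gives the narrowest interval.

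**What to change.** - In SAP 11.4.1, limit zero imputation and the offset to samples taken before the first dose: Day 1 pre-dose in Parts A and C, and Day 1 pre-dose of each period in Part B.
- Use LLOQ/2 for on-treatment troughs below the LLOQ in summaries and plots, as in protocol V4.0. If zero is intended, list it in SAP 1.2 with a reason, after checking against V5.0.
- State one offset value and its unit, and make the shell footnotes agree with it and with the Day 1 limit.
- Add a rule to 11.4.3.3, for example LLOQ/2 in the main analysis with pairs containing a value below the LLOQ excluded as a sensitivity check. Present this as a new SAP choice. It is a real trade-off, as the example shows: LLOQ/2 keeps the low values but can widen the interval, while exclusion removes them selectively.

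The cost is a few sentences of SAP text, one programming condition, footnote edits and one extra sensitivity run. No new data are needed.
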